### **Administration of Surveys**

To compare the training programs on Interventionist uptake, we will conduct pre and post surveys to assess changes in knowledge and assess satisfaction with the training. Survey interviews will be conducted by key personnel via phone or video chat. After obtaining verbal consent from caregivers, caregivers will self-administer a 30-minute REDCap survey. A link will be sent via email to the caregivers. If caregivers prefer to complete the survey on paper, the research team will collect the caregiver mailing address and send via mail along with stamped envelope to be returned to the study team. After the caregiver has completed the self-administered survey, researchers will interview caregivers for up to one hour video chat. The interview will be recorded for quality assurance and research purposes. Data Management Describe how and who manages confidential data, including how and where it will be stored and analyzed. For instance, describe if paper or electronic report forms will be used, how corrections to the report form will be made, how data will be entered into any database, and the person(s) responsible for creating and maintaining the research database. Describe the use of pseudonyms, code numbers and how listing of such identifiers will be kept separate from the research data. We will set up all surveys and tracking forms in REDCap. Interviewers will use an iPad or computer programmed with the survey questions in REDCap to facilitate direct capture of data in real time. We will build in checks to minimize missing and out of range values, which are essential features of REDCap. De-identified data files are entered and stored on the hard drive of the PC of the project statistician if necessary for offsite work, and the DU server. In this way a copy of the data always remain secure in the rare event of fire or computer damage at the central research office. Any identifiable data is only stored on the server and is password protected. This assures that identifiable data cannot be stolen from a laptop or computer. After obtaining caregiver verbal consent, baseline interviews and COPE interventionist sessions will be recorded and saved on the password protect server. Audio recordings will be sent to a HIPAA-compliant Penn-approved third party strictly for the purposes of automatic transcription. After transcription, any identifying information will be removed from documents resulting in anonymous transcripts to be kept on the research office server.

### **Data Management**

We will set up all surveys and tracking forms in REDCap. Interviewers will use an iPad or computer programmed with the survey questions in REDCap to facilitate direct capture of data in real time. We will build in checks to minimize missing and out of range values, which are essential features of REDCap. De-identified data files are entered and stored on the hard drive of the PC of the project statistician if necessary for offsite work, and the DU server. In this way a copy of the data always remain secure in the rare event of fire or computer damage at the central research office. Any identifiable data is only stored on the server and is password protected. This assures that identifiable data cannot be stolen from a laptop or computer. After obtaining caregiver verbal consent, baseline interviews and COPE interventionist sessions will be recorded and saved on the password protect server. Audio recordings will be sent to a HIPAA-compliant Penn-approved third party strictly for the purposes of automatic transcription. After transcription, any identifying information will be removed from documents resulting in anonymous transcripts to be kept on the research office server.

### **Analysis Plan**

Analysis of Aim 1: To compare the training programs on Interventionist uptake. We will conduct pre and

post surveys to assess changes in knowledge and assess satisfaction with the training. COPE interventionists will need to demonstrate Knowledge and Competency in treatment delivery to be certified by Pis and [name] in COPE delivery, a measurement approach we use effectively in our trials (56). We will conduct a noninferiority analysis to determine if online training compared to virtual/remote training results in same or better in Knowledge and Competency scores. Independent-samples t-test, 2 test, and Fishers exact test will be used to compare the groups.

**Analysis of Aim 2:** The fidelity model will be used to compare sessions delivered by interventionists under the two different conditions (online versus virtual/remote training conditions). The accuracy of the computationally derived best model automatic summarization fidelity ratings (excellent, acceptable, problematic) will be evaluated against human ratings for all recorded session (N=600). The comparison of the automated fidelity relative to human fidelity rating will be evaluated through a comparison of agreement (Kappa coefficient). Human ratings will be conducted by Drs [name] and [name] using the COPE Adherence Scale (1= excellent, .5 = acceptable, 0=problematic).

**Analysis of Aim 3:** To compare the efficacy of COPE on participant outcomes. One-sided to-sample t-tests will be used to examine non-inferiority at 4-months. Upper and lower 95% confidence intervals will be presented for means and medians. Assumptions of normality and equality of variance between groups will be evaluated using Shapiro-Wilk and modified Levene's tests, respectively. Should the variances be unequal, the Aspin-Welch unequal variance t-test will be used to examine non-inferiority; should the normality assumption be violated, the non-parametric Mann-Whitney U test will be used to examine non-inferiority. Descriptive statistics including measures of central tendency (mean, median, mode) and variation (standard deviation, interquartile range, range) for continuous measures as well as frequencies and percentages for dichotomous and categorical variables will be run for all measures at each timepoint. Outliers will be assessed by visual inspection of distributions and checked for accuracy. Histograms and Q-Q plots will be used to evaluate assumptions visually. Two-sample t-tests (or non-parametric Wilcoxon tests, as necessary) and Fisher's exact tests will be used to examine differences in demographic and treatment variables between intervention groups at each timepoint. To demonstrate that the online COPE training intervention is the same or better than the virtual/remote training intervention with regards to participant outcomes, one-sided two-sample t-tests will be used to examine non-inferiority at 4 months. Upper and lower 95% confidence intervals will be presented for means and medians. Assumptions of normality and equality of variance between groups will be evaluated using Shapiro-Wilk and modified Levene's tests, respectively. Should the variances be unequal, the Aspin-Welch unequal variance t-test will be used to examine non-inferiority; should the normality assumption be violated, the non-parametric Mann-Whitney U test will be used to examine non-inferiority.

**Consent Process:** All informed consent guidelines of the University of Pennsylvania Institutional Review Board (IRB) will be followed. We will use a multi-stepped approach to gaining consent from Trinity Health PACE occupational therapists and nurses (OT/RNs) using email, DocuSign, PennBox, or mail to obtain consent signatures. The Penn site will obtain consent from OT/RNs who agree to complete the training program. Discussions about consent will take place between the study team and OT/RN participants via phone and video conferencing programs (Skype, FaceTime, Blue Jeans, Zoom, etc.). Two Trinity Health PACE sites will participate in a pilot test of all study procedures. OTs and RNs from these sites will sign the "OT and RN ICF Pilot Test" document. This version of the ICF notes that these participants will participate in the pilot test or beta test. Then, recruitment of caregivers will be done by Trinity research liaisons who will read a Penn-approved recruitment script to caregivers or share flyers with study team contact information to use. Interested caregivers will contact study team members (if received flyer) or be contacted via telephone by Penn study team members (if consented to have their contact shared) who will provide more detail about the study, answer questions, and read the caregiver verbal consent script. Within the script is language that informs the caregiver that 1) the

OT and research team will record and transcribe COPE sessions and interviews with dyads for quality and assurance purposes, and 2) the research team will collect patient data from the Trinity Health PACE medical record for research purposes. The objectives, procedures, and a clear statement explaining risks and benefits of this study will be presented via the consent script. Caregivers who consent verbally will be emailed or mailed a copy of the consent script which has been signed by the Penn researcher obtaining consent. If caregivers consent to participant, caregivers will be screened for eligibility. Caregivers will be informed that the screen is confidential and completely voluntary. All call notes, consent forms and telephone screens will be performed and housed in REDCap or on a Penn-approved secure server. Penn will house all recruitment and consent forms and assume responsibility for any and all modification of ICFs. For those initially eligible based on the telephone screen and who consent to participate, a full baseline telephone interview will be conducted either following the screen or at a time more convenient for the caregiver but within one week of completing the screen.

Regardless of when the baseline interview is conducted, the interviewer will again obtain verbal consent from the family caregiver for their participation. Participants who currently active or in the follow-up stage will need to re-consent to participate. Caregivers who originally consented prior to September 18th, 2022, will be called and read the additional information added to the consent form and asked if they have any questions. Once all questions have been answered, caregivers will be asked to verbally consent. Once confirmation of consent is received over the phone, caregivers will receive an updated copy of the written statement of research. Staff participants (occupational therapists and registered nurses) who have signed consent forms prior to September 16th, 2022 will need to be re-consented. These participants will receive an email with the new consent language listed and a blank copy of the updated consent form attached. Staff participants will be asked to follow up with any questions they have. If participants do not have questions or all questions have been answered, participants will be asked to sign the form and send back to Penn researchers.

**Study duration:** Caregivers The study will take place over a period of 4 months. This means that COPE dyads (persons with memory problems and their caregivers) will receive up to 10 1-hour sessions over the course of 4 months by an occupational therapist; and up to two face-to-face or virtual visits and 1 telephone session by a registered nurse. We anticipate enrolling 50 participants from 10 Trinity Health PACE organizations. RNs/OTs: The educational portion of the study will be 16 hours in length. For OTs, the implementation portion of the study will consist of up to 10 one-hour home visits over a 4-month period during the year in which the dyads are recruited and participate in the COPE intervention. For RNs, the implementation portion will consist of up to 2 two-hour clinical evaluation in-home or virtual visits with each PACE dyad soon after they are enrolled in the COPE program.

**Risk / Benefit Assessment:** There are only minimal risks associated with this study. It is anticipated that caregivers will experience more benefits than risks from their participation in this study. Caregivers in the intervention group will potentially benefit by receiving on-going support, learning specific techniques for managing their own stress, disease education and by having unmet needs identified and managed. Older adult clients of caregivers in the COPE Program may benefit indirectly from the techniques and understandings their caregivers obtain. All families receive the COPE Program; one group will receive the COPE Program from OT/RNs trained via an online simulation approach; another group will receive the COPE Program from OT/RNs trained via video conference training conducted by a trained OT.

**Data and Safety Monitoring:** Although this is a minimal risk study and a Phase IV effectiveness trial (NIA Stage I), we propose to develop an independent Data and Safety Monitoring Committee (DSMC) to assure participant safety and adherence to human subject protection policies. We plan to identify a 3 to 5-member DSMC of individuals with different types of expertise covering practical trial methodologies, mixed method designs, long-term care services, and dementia care. Here we outline our proposed plan for data and safety monitoring, key responsibilities of members, time of meetings, and schedule for and content of major reports

to be provided to the DSMC for this proposed trial. Primary responsibilities: The DSMC will be responsible for reviewing the safety of study participants during the conduct of this study and provide recommendations to the research team on specific aspects of the research protocol as it pertains to safety, potential study alerts and adverse events. Specific responsibilities of the DSMC will be to: a) provide an independent periodic review of recruitment and enrollment progress; b) review adverse events (AEs) including serious events and offer recommendations regarding the trial based on such observed events; c) serve in a consultative capacity to the research team regarding study procedures to address ethical dilemmas (e.g., reporting of abuse), safety of subjects in the trial, and appropriateness of all study procedures. Composition of the DSMC: The DSMC will be an independent multi-disciplinary group consisting of biostatistical, applied research and clinical experts who collectively have experience in practical trial designs, multi-site trials and mixed methods. The 3 to 5 member board will have no apparent conflict of interest with the investigative team or study including financial, scientific or regulatory in nature. DSMC members will be responsible for advising the PIs of any changes in their relationship and/or financial interests that occur during the course of the trial. The DSMC and PIs will be responsible for deciding whether these changes create a conflict of interest. Any DSMC member who develops a conflict of interest during the course of the trial will be asked to resign from the DSMC and another person with similar areas of expertise will be sought. Otherwise, DSMC membership is to be for the duration of the trial. DSMC Meetings, Documentation: We propose that the DSMC have one face-to-face meeting prior to entering into the field for the trial and one teleconference call each subsequent year unless the DSMC decides and votes otherwise at its first organizational meeting. More frequent meetings or teleconferences may be held in the rare need to review serious adverse events from the trial at the discretion of the DSMC. At the initial meeting in year 01 (anticipated to occur in month 5 prior to entry into the field), the DSMC will review all study procedures including data collection forms, intervention protocol and oversight plan. At this meeting, the DSMC will agree on whether there should be interim analyses, and if so, the stopping rules and interim analysis plan that avoids potentially biasing the investigative team. Modifications to protocols based on the DSMC review will be made prior to entering the field. At subsequent conference calls, the DSMC will review the progress of the study (accrual rate, protocol deviations and interim study analyses if recommended) and make recommendations. A representative of the research team will keep minutes of these meetings. A copy of the minutes approved by the DSMC will be shared with the IRB of UPENN. The minutes will include recommendations of the DSMC and be provided to the NIH after each meeting. Meetings of the DSMC will be open unless the DSMC requests otherwise. A closed meeting of the DSMC may be requested if it is deemed necessary to review outcomes data. The DSMC chair or their designate will take meeting notes of closed sessions. Provision of Data for DSMC Review. Interim Analyses: We elect not to consider interim analyses in this study due to the extended time for recruitment and the low likelihood of a sufficiently large effect that would make it possible to stop early. This study is designed as a non-inferiority trial in which two different training methodologies are being evaluated. Outcomes of the COPE program for people with dementia and caregivers are secondary and serve to confirm (or not) whether the online training approach is as good or better than traditional face-to-face intensive training. However, we will revisit this decision with the DSMC at its first organizational meeting. Adverse Event (AE) Reporting: The DSMC will be notified by the PI of any serious AE within 48 hours of initial notification to the project team that is attributed to the intervention (low or high probability). All members of the DSMC will receive copies of all safety reports at the time of their submission to the IRB. Safety Monitoring Plan: We do not anticipate any adverse reactions to the training approaches or implementation of the COPE program. Based on our previous work and studies in this area by others, there is only a small risk that family caregivers or persons with dementia will become increasingly anxious to the point that it becomes an adverse event (e.g., harmful to self or others) as a consequence of the COPE program. However, interviewers/ interventionists will be well trained to manage this reaction or make an effective referral if necessary and documentation of all such events will occur. Recruitment and AE Reports: Reports presented to the DSMC will include data on enrollment (study accrual by month; comparison of expected to actual enrollment; number of individuals screened, number eligible and number ineligible, number randomized by gender, and AEs. Also, the DSMC will receive reports of the number of study participants who discontinue from each study arm (those receiving COPE from interventionists trained via face-to-face/virtual versus those receiving COPE from interventionists trained via online program) and/or the study and reasons for discontinuation. We propose that reports be provided to the DSMC twice yearly. However, the DSMC will decide upon the schedule of

reports at their first organizational meeting. Also, the DSMC may request reports as needed as well as the unblinding of the data should they deem this necessary. If unblinded outcome data is required, the biostatistician for this study ([name]) will serve as a liaison for the PIs, database and the DSMC in order to assure that the PI and the investigative team remains blinded. For the first meeting of the DSMC, members will receive and review the following materials: a) Grant proposal, relevant appendices, reviewers comments; b) our quality control procedures c) IRB approved verbal assent scripts; d) Telephone screen, baseline and follow-up batteries; e) Shell of Access data base for management of interview schedules and enrollment information; f) Subject tracking forms; g) Adverse event procedures and forms; h) Intervention treatment documentation forms; i) Shell for reporting recruitment and enrollment; j) Data shells for reporting tracking information and baseline characteristics; k) Decision rules for intervention termination (e.g., death, extended hospitalization, relocation, nursing home placement); l) Protocols, data collection kits, participant information for salivary biomarker data collection.

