serve as the control site in which training will be provided via the virtual/remote training lead by a trained OT; 5 PACE organizations will serve as the comparison and be trained through the online training site. Prior to randomization, we will carefully examine PACE organizations on important variables such as size, location (urban; rural) percent of persons with dementia, and staff: participant ratio. In each site, one occupational therapist (OT) and one nurse (RN) will be trained (e.g., 5 OTs and 5 RNs in virtual/remote training sites; 5 OTs and 5 RNs in online training sites for a total of 10 OTs and 10 RNs or 20 health providers) Re-randomization procedures. Because COPE will be delivered by PACE staff to multiple participants with dementia within each organization, randomization at the individual participant level could lead to significant contamination between treatment and control conditions within an organization. Prior to randomization, we will collect organization-level data and have measures of organization size (or capacity), location (urban, suburban, rural), and summary characteristics of the participant population at each organization (e.g., percentage with dementia diagnosis, percentage minority). Because we will randomize ten organizations to five virtual/remote and five online training organizations, notable and problematic imbalances on at least a few organization-level characteristics could easily occur by chance in a single randomization. Methodological innovations are needed to achieve balance on these multiple organization-level characteristics while still maintaining the experimental rigor and inferential value of true random assignment. [name] will implement a re-randomization approach to achieve these important methodological goals. The balance match weighted (BMW) design is an innovative re-randomization procedure that is particularly well suited to our goals (54). Using the BMW approach, we will: 1) finalize the list of important covariates for which we desire matching or balancing across intervention and control organizations, 2) generate 20 lists of random assignments for these 10 organizations into intervention and control conditions, 3) calculate propensity scores of intervention assignment as a function of the covariates, and 4) select the random assignment list that minimizes the propensity score differences between intervention and control organizations. The BMW approach provides a random assignment distribution that has an optimal balance on multiple organization-level characteristics. This will result in even greater control over potential covariate influences and provide somewhat greater power to detect a COPE program effect. Treatment Conditions: COPE Online Training: Trinity PACE Organizations assigned to the COPE Online Training will receive the 10- Module training program described above. Designated OT/ RNs at the assigned PACE Organization will be emailed unique log-in details and instructions for completing the online training within the 3-day training window (to align with control group training) but at their own pace. Log-in details including date, time and duration in training sessions will be tracked. COPE Virtual/Remote Training: We will train one OT and one RN at each of the five PACE organizations randomly assigned to the virtual/remote training. [name] will conduct trainings. Our training program will involve up to 3 days which include about 4 hours of initial readings, PowerPoint presentations, and case presentations. Training will take place via web conference (via GoToMeeting.com or other platform) sessions. We will offer three of these training sessions to accommodate COPE staff members' schedules and assure an interactive process. Further, interventionists will participate initially in monthly tele-conference or web conference sessions and then 6 times a year over the duration of intervention delivery. Sessions will involve case presentations, troubleshooting, and adherence monitoring. We have used this approach in multi-organization endeavors with up to 15 interventionists actively participating by telephone. Using a structured agenda and assigning case presentations a priori facilitates productive discussions. We have allocated funds for COPE staff members time to participate in training and follow-up bimonthly calls to troubleshoot cases. Both groups will participate in monthly debriefing sessions which will be recorded and used to understand type of questions asked, problems encountered etc., to compare the two training groups. We have a specific agenda and methodology for interventionists to provide case reports (55). We will also establish a password secure and encrypted email list serve for interventionists to post challenges and receive feedback from PIs and other interventionists.

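### The Aim 1 t-test on 10 versus 10 staff ignores that sites are randomized and each trains one OT and one RN, so its standard error can be wrong in either direction

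*Combined protocol and SAP*

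**What the plan says.** The Analysis Plan, under Aim 1, states the objective as follows: "We will conduct a noninferiority analysis to determine if online training compared to virtual/remote training results in same or better in Knowledge and Competency scores". The method is one sentence: "Independent-samples t-test, 2 test, and Fishers exact test will be used to compare the groups". The second test named is presumably the chi-square, its symbol lost in conversion. The sentence does not tie tests to outcomes. I take the t-test to be meant for the two scores. The Research Plan carries the same Aim 1 analysis with the comparator described as face-to-face training.

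The design is set out in Study Procedures, Phase 2. On allocation: "Because we will randomize ten organizations to five virtual/remote and five online training organizations". On staff: "In each site, one occupational therapist (OT) and one nurse (RN) will be trained", which gives "5 OTs and 5 RNs in virtual/remote training sites; 5 OTs and 5 RNs in online training sites".

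The text available for this review contains no discipline term and no allowance for site in the Aim 1 analysis. It also gives no margin, significance level, SD, expected OT-RN difference or within-site correlation for Aim 1. One-sided testing is stated only for Aim 3: "One-sided to-sample t-tests will be used to examine non-inferiority at 4-months".

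**The concern.** The t-test treats the 20 scores as two simple samples of 10. The design departs from that in two ways.

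- **Discipline is balanced by design.** Each arm has five OTs and five RNs, so a difference between the professions cancels from the arm difference. It still enters the t-test's pooled variance and widens the interval.
- **Site is the randomized unit.** The OT and RN at a site share an employer and are always in the same arm. If their scores are positively correlated, the 20 scores carry less information about the arm difference than the t-test assumes, and the interval is too narrow.

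A non-inferiority conclusion rests on where one confidence limit falls. An interval that is too wide can miss non-inferiority that is there. One that is too narrow can declare it wrongly, which is the more serious error.

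**Working it through.** **The plan's own figure.** 10 sites × (1 OT + 1 RN) = 20 staff, or 5 OTs and 5 RNs per arm. This reproduces. No Aim 1 power calculation is given to check.

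**Inputs.** From Study Procedures: 5 sites per arm, one OT-RN pair per site. Assumed, because the documents give no values: d, the OT-RN gap in within-discipline SDs (0 to 1.5); rho, the correlation between the two staff at a site (0 to 0.3); and an illustrative margin of 1 SD at one-sided 5%. The within-discipline variance is set to 1.

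**True variance of the arm difference.** A site mean has variance (1 + rho)/2, and an arm averages five of them. The difference between arms has variance 2 × (1 + rho)/10 = 0.2(1 + rho).

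**Variance the t-test reports, on average.** Within an arm of 10, the expected sample variance is [10 + 10(d/2)² − (1 + rho)]/9 = 1 − rho/9 + 5d²/18. Multiplying by 2/10 gives 0.2(1 − rho/9 + 5d²/18).

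**Direction of the error.** The reported variance exceeds the true one when 5d²/18 > rho + rho/9 = 10·rho/9, that is, when d² > 4·rho. The thresholds are d = 0.45 at rho = 0.05, 0.63 at 0.1, 0.89 at 0.2 and 1.10 at 0.3.

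**Independent staff (rho = 0).** The planned 95% interval relative to one adjusted for discipline has width ratio √(1 + 5d²/18) × t(18)/t(17) = √(1 + 5d²/18) × 2.101/2.110:

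| d | Width ratio |
|---|---|
| 0.1 | 0.997 |
| 0.2 | 1.001 |
| 0.5 | 1.030 |
| 1.0 | 1.126 |
| 1.5 | 1.269 |

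Break-even is d of about 0.17. Below that, the lost degree of freedom outweighs the gain.

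**Simulated type I error, nominal one-sided 5%:**

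| rho | d | Planned t-test | Arm + discipline, no site | Site means, 8 df |
|---|---|---|---|---|
| 0.1 | 1.0 | 3.9% | 5.9% | 5.0% |
| 0.2 | 0 | 6.8% | 6.7% | 5.0% |
| 0.2 | 0.5 | 6.1% | 6.7% | 5.0% |
| 0.2 | 1.0 | about 4.5% | 6.7% | 5.0% |
| 0.3 | 1.0 | 5.3% | 7.5% | 5.0% |

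At rho = 0.2 and d = 1.0 the planned test is near its nominal level only because the two errors happen to offset: its average reported SE is √[0.2(1 − 0.022 + 0.278)] = 0.501, against a true 0.490.

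**Power at the 1-SD margin, rho = 0.** The planned test has 69%, 61% and 52% at d = 0, 1.0 and 1.5. The site-mean test does not depend on d. Its noncentrality is 1/√0.2 = 2.24 on 8 df, giving about 65%. At rho = 0.2 it is 1/√0.24 = 2.04, giving about 59%.

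**The case against.** The case for leaving the plan alone has real force.

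- **No gap is documented.** The Study duration section gives OTs up to 10 sessions per dyad and RNs far fewer contacts, and a reader might infer that a score difference is likely. Those figures describe delivery workload, not test scores. Within an arm both professions receive the same training, and both must show Knowledge and Competency to be certified, which may narrow any gap. This stands.
- **Change scores may be what is analysed.** The plan has "pre and post surveys to assess changes in knowledge and assess satisfaction with the training". If change is the outcome, a stable OT-RN gap cancels within person, and d becomes the difference in gain. The text does not settle this. It weakens the discipline half of the point but leaves the site half untouched.
- **The planned test can be conservative.** With independent staff and a gap, it errs on the safe side and costs only power. That is true at rho = 0 but not in general, and nothing in the documents puts rho at zero for two colleagues at one organization.
- **The site analysis has fewer degrees of freedom.** This also stands. At rho = 0 with no gap, it gives up about 4 points of power.
- **The missing margin matters more.** Until Aim 1 has a margin, success is undefined. That is a separate and larger gap, but it does not make the standard error right.

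A reader might also infer that the comparison will be confounded by profession. The plan trains one of each at every site, so that arises only if a pair is incomplete.

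**Conclusion.** The point holds: the Aim 1 t-test does not match the design, and its standard error is correct only by coincidence of d and rho. If staff are independent, the cost is a wider interval, by about 3%, 13% or 27% at gaps of 0.5, 1.0 or 1.5 SD, and nothing below about 0.17 SD. If scores correlate within site and the gap is small, the cost is excess false claims of non-inferiority, about 6.8% against 5% at rho = 0.2 and d = 0. The values of d and rho are assumptions, as are the 1-SD margin and the 5% level used for the error rates and power.

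A reader might infer that any OT-RN difference makes the error bars too wide, and that a discipline covariate alone would cure this. The documents support neither. The standard error is too large only if d² > 4·rho. Adding discipline without site removes the inflation that was masking the clustering: at rho = 0.2 and d = 1.0, error rises from about 4.5% to 6.7%.

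**What to change.** For Knowledge and Competency, replace the independent-samples t-test with one of the following, named in advance:

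- a comparison of the ten site means, averaging the OT and RN score at each site (5 versus 5, 8 df); or
- a linear mixed model with arm and discipline as fixed effects, site as a random effect, and small-sample degrees of freedom. With complete pairs this is equivalent to the site-mean analysis, provided the estimated site variance is not truncated at zero. It can also be used if a site supplies only one profession.

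Do not add discipline without site. State whether the outcome is the post-training score or the change. Report the OT and RN arm differences side by side, descriptively, to show whether one profession offsets the other.

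The cost is a few lines in the Analysis Plan and no new data, since site and profession are known for every trainee. The price is degrees of freedom, 8 instead of 18. Under the illustrative margin, power is about 65% at rho = 0, which is below the planned test's 69% with no gap but above its 61% at a 1-SD gap, and about 59% at rho = 0.2. In return, the error rate is held at 5%.
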